## **CLINICAL INVESTIGATION PLAN (CIP) SYNOPSIS**

**INVESTIGATION TITLE:**

**Multicentre, prospective, randomized, open-label, assessor blinded study to evaluate Granulox® used as adjunct therapy to defined standard of care vs. defined standard of care for the treatment of predominantly chronic venous leg ulcers (VLU)**

## Objectives

## Primary Objective

The primary objective of this study is to compare wound healing of chronic venous leg ulcers (VLUs) managed using standard of care, with or without added Granulox®, at up to 20 weeks post therapy initiation. The main efficacy criteria is Confirmed Complete wound Closure (CCC).

## Secondary Objectives

Term	Percentage
GMOs	75%
Organic	95%
Natural	85%
Artificial	35%
Organic	98%
Natural	90%
Artificial	40%
Organic	92%
Natural	88%
Artificial	25%

## Clinical Investigation Design

This is a N = 254 patient, European, multi-centre, assessor blinded, 2-arm, randomised controlled study. The study will include multiple European countries (e.g. France, Germany, UK, Poland, Hungary, Croatia and Czech Republic), with approximately 2-7 clinics per country.

The study will run with a two-phase set-up, with a 14 days run-in period and an up to 20 weeks treatment period starting with randomization and allocation of treatment.

## Endpoints

## Efficacy Endpoints

The following efficacy endpoints will be assessed and evaluated in the study:

- Confirmed Complete wound Closure (CCC); derived by two blinded quantifications of 100% re-epithelialization by PictZar® 15 days (+/- 3 days) apart

■ [REDACTED]

■ [REDACTED]

Investigation Code Granulox01 Final Version Approval date 2019-10-24

## Safety Endpoints

Adverse Events (AE) and Serious Adverse Events (SAE) will be collected in the study to measure safety associated to study treatments from ICF signature until study completion. AEs will be assessed according to criteria for Adverse Device Effect (ADE), SAE, Serious Adverse Device Effect (SADE), and Device Deficiencies (DD).

## Inclusion Criteria

1. Signed consent to participate.
2. No planned hospitalization in the forthcoming 20 weeks.
3. Male or female (women of childbearing age must have an acceptable method of birth control).
4. Age >18 years.

**Investigation Code** **Granulox01** **Final Version** **Approval date** **2019-10-24**

---

5. Recent (less than 12 months) doppler or duplex colour ultrasonography compatible with chronic venous insufficiency.
6. ABPI (less than 3 months)  $\geq 0.7$  for both legs. If ABPI  $> 1.4$ , then big toe pressure  $> 60$  mmHg is required or an alternative measurement verifying normal distal arterial flow.
7. At least one or more supra- or peri-malleolar leg ulcers and no foot ulcer or another chronic wound.
8. In case of two ulcers, select ulcer with the highest PUSH score at randomization and treat the non-selected ulcer in the same way as ulcers in the control group.
9. In case of two ulcers on the same limb, ensure that the distance between each ulcer is 3 cm as measured from the margins of each ulcer that are closest to one another.
10. Wound duration  $> 8$  weeks and  $< 60$  months.
11. At randomization, the ulcer area should be  $3 \text{ cm}^2 - 70 \text{ cm}^2$  and should not have decreased by more than 30% during the 2-week run-in period.
12. Less than 50% of the wound area should be covered with fibrinous tissue at randomization and after debridement.
13. Patients considered as compliant/adherent to the compression device during the run-in period (i.e. no more than 2 days without compression over the 2-week run-in period).
14. No clinically significant comorbidities requiring the use of systemic steroids or any cytotoxic or immunosuppressive agents.

### **Exclusion Criteria**

1. Infected ulcer according to the judgment of the investigator defined as any wound condition requiring the prescription or continuation of systemic antibiotic therapy at randomization.
2. Circumferential wounds.
3. Wound covered fully or partially by necrotic tissue (black tissue).
4. Patients who will have problems following the protocol, especially compression therapy.
5. Patients included in another on-going clinical investigation, or patients who have participated in a clinical investigation during the past 30 days.
6. Wounds treated with dressings containing an active component (e.g. silver, nano-oligosaccharide factor (NOSF), charcoal, chlorhexidine, iodine or ibuprofen) 14 days prior to study enrollment.
7. Patient with a systemic infection not controlled by suitable antibiotic treatment.
8. Current treatment with radiotherapy, chemotherapy, immunosuppressant drugs or high doses of oral corticosteroids ( $> 10$  mg Prednisolone or equivalent) if any.
9. Patient with deep vein thrombosis within 3 months prior to inclusion.
10. Known allergy/hypersensitivity to the ingredients of the dressings and/or Granulox®.
11. Malignant wounds.
12. Endovenous surgery planned or performed within the past 30 days.

13. Primary lymphoedema caused by congenital/developmental defect, i.e. Milroy's disease (congenital lymphedema), Meige's disease (lymphedema praecox), or Late-onset lymphedema (lymphedema tarda).

### Investigational Device and Comparator

#### Granulox®

Granulox® is a CE marked medical device manufactured by HÄLSA Pharma GmbH. It is a topical haemoglobin spray, which is designed to transport oxygen to the wound site. In the study, Granulox® will be used as intended, in addition to defined standard care. The following procedural steps should be followed:

1. After wound bed preparation (e.g. debridement and cleaning) Granulox® should be sprayed onto the cleaned wound until the wound is completely coated with a thin film. That is, hold the nozzle about 5 to 10 cm from the wound and spray until the wound is completely coated with a thin film. 1 to 2 seconds are normally sufficient to cover a wound area of 2 x 3 cm.
2. After Granulox® has been applied, the wound should be covered with a breathable wound dressing containing no active ingredients.
3. Granulox® should be applied again every time the dressing is changed, but at least every three days.

#### Standard of care:

VLU standard of care treatment will be performed according to local practice requirements but reapplied at least every third day until complete epithelization. Standard of care will include the following:

1. Wound bed preparation, i.e.:
  - Careful wound cleansing with water, saline, Ringer's solution or preserved mechanical wound cleansers (i.e. polyhexanide (Prontosan, Lavanid), or hypochlorous (Granudacyn, Microdacyn) irrigation)
  - Wound debridement if necessary and as per standard of care (e.g. mechanical or surgical debridement)
2. Application of appropriate breathable wound dressing which must be selected among the following categories and with regard to routine local care, level of exudate, and healing stage:
  - Hydrofiber: Exufiber, Aquacel Extra
  - Foam dressings: Mepilex XT, Mepilex Lite, Biatain Soft Hold, Biatain Silicone lite, Aquacel Foam, UrgoTul Lite
  - Wound Contact layer: Mepitel, Mepitel One, Adaptic Touch, UrgoTul
  - Superabsorbant: Mextra, Kiliniderm Superabsorber, Zetuvit Plus/Resposorb
3. Application of appropriate compression therapy which must be selected among the following categories and with regard to routine local care, level of exudate, and healing stage:
  - Multilayer compression: [REDACTED]
  - Hosiery and stockings compression: [REDACTED]  
[REDACTED]

NB: Dressings including active components are not allowed. Within a clinic, there must be consistency in the choice in dressings, i.e. the same sequence of dressings should be kept for all the patients.

3. Application of appropriate compression therapy which must be selected among the following categories and with regard to routine local care, level of exudate, and healing stage:

- Multilayer compression: [REDACTED]
- Hosiery and stockings compression: [REDACTED]  
[REDACTED]

- Short stretch bandages

NB: A multilayer compression system is preferred and consistency in compression therapy throughout the study is mandatory, unless patient compliance issues necessitate change. Patients must be withdrawn from study in case of severe non-compliance to compression therapy.

## LIST OF APPENDICES

*Appendix A F-449 Clinical Investigation Plan Appendix A, Core Signatures  
F-583 Clinical Investigation Plan Principal Investigator Signature*

*Appendix B Master Subject Information and Consent Form*

*Appendix C F-542 All variables to be obtained during the Investigation*

*Appendix D Assessment tools/questionnaires; PUSH, Wound-QoL, EQ-5D-5L, and NRS.*

*Appendix E Instructions for use Granulox®*

## LIST OF ABBREVIATIONS

ADE	Adverse Device Effect
AE	Adverse Event
CCC	Confirmed Complete wound Closure
CIP	Clinical Investigation Plan
CP	Conditional Power
CRF	Case Report Form
CVI	Chronic Venous Insufficiency
DD	Device Deficiency
EC	Ethics Committee
EQ-5D-5L	EuroQol.org - 5 dimensions - 5 level instrument to describe and value health
FAS	Full Analysis Set
HRQoL	Health-Related Quality of Life
IARC	Interim analysis review committee
IRB	Institutional Review Board
NRS	Numerical Rating Scale
PCC	Possible Complete wound Closure
PP	Per Protocol
PRO	Patient Reported Outcome
PUSH	Pressure Ulcer Scale for Healing
RA	Regulatory Authority
SAE	Serious Adverse Event
SADE	Serious Adverse Device Effect
WAR	Wound Area Regression
50WAR	50% Wound Area Regression

---

**Investigation Code** **Granulox01** **Final Version** **Approval date** **2019-10-24**

---

**90WAR** **90% Wound Area Regression****VLU** **Venous Leg Ulcer****Wound-QoL Wound Quality of Life questionnaire**

## 1. INTRODUCTION

Venous leg ulcer (VLU) is a severe clinical manifestation of chronic venous insufficiency (CVI) and is responsible for about 70% of chronic ulcers in the lower limbs. VLUs are a major health problem because of their high prevalence and associated high cost of care.

Compression therapy is the most widely used conservative treatment for VLUs as the application of external pressure to the calf muscle raises the interstitial pressure resulting in improved venous return and reduction in the venous hypertension. Published healing rates of VLUs obtained with compression therapy vary widely from 40-88%. Over a quarter of patients with VLUs fails to heal despite standard of care including compression therapy, and those who do heal often take 6 months or longer. Risk factors, such as wound age and size, have been identified to be correlated with the failure of VLUs to heal, showing VLUs present for at least 5 months prior to appropriate management and whose area is 10 cm^2 or larger, have less than 20% chance to heal at 24 weeks.

Granulox® is a haemoglobin spray that can be added to standard of care of chronic wounds. It is expected to improve the tissue repair process by increasing tissue oxygen supply. In a previous randomized controlled trial (RCT) comparing Granulox® to a control group in VLUs, a significant mean reduction of the wound surface area was observed at 13 weeks with a decrease of 53.4% (p<0.0001) for Granulox® treated wounds. Use of Granulox® was associated with significant pain score reduction compared to standard wound care alone thus improving patients' quality of life. Furthermore, use of Granulox® as an adjunct therapy led to a significant reduction of slough and recurrence compared with standard care alone.

[figure not shown]
This study is intended to assess the healing benefits of Granulox® therapy in combination with standard of care for the management of chronic VLUs over a period of 20 weeks, compared to VLU standard of care treatment without Granulox®.

## 2. OBJECTIVES AND HYPOTHESES

### 2.1 Primary Objective

The primary objective of this study is to compare wound healing of chronic VLUs managed using standard of care, with or without added Granulox®, at up to 20 weeks post therapy initiation. The main efficacy criteria is Confirmed Complete wound Closure (CCC).

### 2.2 Secondary Objectives

### 3. INVESTIGATION PLAN AND PROCEDURES

#### 3.1 Clinical Investigation Design

This is a N = 254 patient, European, multi-centre, assessor blinded, 2-arm, randomised controlled study. The study will include multiple European countries (e.g. France, Germany, UK, Poland, Hungary, Croatia and Czech Republic), with approximately 2-7 clinics per country.

The study will run with a two-phase set-up, with a 14 days run-in period and an up to 20 weeks treatment period starting with randomization and allocation of treatment.

#### 3.2 Procedures and Assessments

This study starts with a 14 days run-in period to verify two of the required inclusion criteria, i.e. that the wound area does not decrease more than 30% during run-in period and compliance to compression therapy part of standard of care.

After the 14-days run-in period during which time patients will receive standard of care, (D-14 to D0) patients meeting the selection criteria will be randomly allocated (on D0) to experimental (i.e. standard of care plus Granulox®) or control (i.e. standard of care only) groups.

Randomization will be stratified on study site, wound duration (<5 months; ≥5 months), and wound area after run-in period (<10; ≥10 cm^2), to ensure equal distribution of test and control in these sub-groups. This, as wound duration and wound area may significantly impact outcomes, and as minor variations in standard of care between study sites may still be present in spite of the measures taken to ensure standardization. See details on standardization of standard of care in Section 3.5.

Each patient will be followed to wound closure, or up to 20 weeks (whichever occurs first), with scheduled clinical visits at 1 week (W1), 4 weeks (W4), 8 weeks (W8), 12 weeks (W12), 16 weeks (W16), and 20 weeks (W20). Additional visits are allowed in between the per-protocol scheduled visits. If suspected wound closure occurs at any point during the study, a final assessment visit will be scheduled 15 days (±3 days) subsequent to the suspected wound closure observation to verify CCC. If wound closure is confirmed, the study is completed for this patient. If wound closure is not confirmed, the patient should continue to be followed according to the schedule of assessments. See study Flow Chart at Section 3.2.1 and Schedule of Assessment at section 3.3.8.

In between clinical visits, wound management will follow standard of care. Home visits will be performed by study nurses who are responsible for changing dressing, reapplying Granulox® (for patients randomized to the treatment group only), and reapplying compression therapy. See details in Section 3.5.1.1. Home visits frequency will follow local practice requirements but must take place at least every 3rd day until epithelization is complete. The study nurse will record information in the patient-specific diary. If considered necessary, nurses can ask for an additional patient visit to the investigating centre. This is mandatory at suspected complete wound closure.

If at any time, a wound graft is required (it usually requires at 24-48 hours hospitalization), study will not be considered as completed and patients will still be followed according to the schedule of assessments (even if experimental treatment is no longer applied) up to CCC occurrence or up to W20 (whichever occurs first).

[figure not shown]
The study will be stopped before W20 for a given patient in the event of:

- Consent withdrawal
- Impossibility to follow the patient (i.e. lost to follow-up)

- Hospitalization of more than 48h for any reason other than wound graft
- Death
- Reach of endpoint and study completion, i.e. CCC.

In any other cases, including the cessation of experimental treatment for any reason, patient will continue study visits as per schedule of assessment. See details on analyses sets in Section 5.2.1.

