### **3.4.3 Method of Assigning Subjects to Treatment Groups**

At initial screening and after an informed consent signature is obtained (day-14), an enrolment number is assigned to each patient who agrees to take part in the study. Following the run-in period, and after all eligibility criteria have been confirmed (day 0), randomisation is initiated and treatment allocated to either standard of care only (control group) or standard of care and Granulox® (test group).

Randomisation is centralized and stratified according to:

- Wound duration (<5 months;  $\geq$ 5 months)
- Wound area after run-in period ( $<10 \text{ cm}^2$ ;  $\geq 10 \text{ cm}^2$ )
- Country

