### **5.2.2 General statistical methodology**

This study will use confirmative and explorative analyses. All confirmative analyses will be based on FAS. Confirmative analysis of primary variables will also be performed based on PP.

Imputing of missing data in outcome variables will generally be used. For confirmative analyses, multiple imputations with Fully Conditional Specification (FCS) will be used for primary efficacy analysis. Confirmative secondary analysis and exploratory analyses will use stochastic imputation with FCS. Missing data on demography and background variables will not be replaced.

The study include testing analysis of the primary variable and sequential testing of selected secondary variables for confirmative analysis.

The study utilized stratified randomization based on site, wound size, and wound duration. This is reflected by a stratified primary analysis adjusted for these variables. For adjusted comparison between the two randomized groups, multivariable logistic regression will be used for dichotomous variables and analysis of covariance for continuous variables.

Continuous variable will be described with mean, SD, median, minimum and maximum and categorical variables with numbers and percentages. For unadjusted and adjusted analyses, mean differences with 95% CI will be calculated. For dichotomous variables, for descriptive purpose, relative risk with 95% CI will also be calculated. All significance analyses will be two-sided and conducted at the 5% significance level.

For unadjusted comparison between the two randomized groups Fisher's exact test will be used for dichotomous variables, Fisher's non-parametric permutation test for continuous variables, Mantel-Haenszel chi-square test for ordered categorical variables, and Chi-Square test for non-ordered categorical variables.

Applicable descriptive statistics and non-parametric statistical test methods are used to describe and explore secondary variables. For explorative analyses, no multiple-test considerations are made. For time to endpoint outcomes the Kaplan-Meier model and logrank test are used unadjusted and Cox proportional hazard model for adjusted analyses.

[figure not shown]

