### **5.2.2.1 Primary efficacy analysis**

The primary analysis of comparison of CCC between the two randomized groups will be using binary logistic model at significance level 0.05, on FAS with multiple imputation including the following covariates:

1. Country (as fixed effect)
2. Wound duration (<5 months;  $\geq$ 5 months)
3. Wound area after run-in period (<10 cm^2;  $\geq$ 10 cm^2)

Sensitivity analysis will be comparison between the two randomized groups unadjusted on CCC with Fisher's exact test without imputation.

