#### 1.2.1 Procedures and Assessments

This study starts with a 14 days run-in period to verify two of the required inclusion criteria, i.e. that the wound area does not decrease more than 30% during the run-in period and compliance to compression therapy part of standard of care.

After the 14-days run-in period during which time patients will receive standard of care, (D-14 to D0) patients meeting the selection criteria will be randomly allocated (on D0) to experimental (i.e. standard of care plus Granulox®) or control (i.e. standard of care only) groups. Randomization will be stratified on country, wound duration (<5 months;  $\geq$ 5 months), and wound area after run-in period ( $<10$ ;  $\geq 10$  cm $^2$ ), to ensure equal distribution of test and control in these sub-groups. This, as wound duration and wound area may significantly impact outcomes, and as minor variations in standard of care between study sites may still be present in spite of the measures taken to ensure standardization.

Each patient will be followed to wound closure, or up to 20 weeks (whichever occurs first), with scheduled clinical visits at 1 week (W1), 4 weeks (W4), 8 weeks (W8), 12 weeks (W12), 16 weeks (W16), and 20 weeks (W20). Additional visits are allowed in between the per-

Protocol: Granulox01	Protocol No:
	Version: D1.0

protocol scheduled visits. If suspected wound closure occurs at any point during the study, a final assessment visit will be scheduled 15 days ( $\pm 3$  days) subsequent to the suspected wound closure observation to verify CCC. If wound closure is confirmed, the study is completed for this patient. If wound closure is not confirmed, the patient should continue to be followed according to the schedule of assessments.

In between clinical visits, wound management will follow standard of care. Home visits will be performed by study nurses who are responsible for changing dressing, reapplying Granulox® (for patients randomized to the treatment group only), and reapplying compression therapy. Home visits frequency will follow local practice requirements but must take place at least every 3rd day until epithelialization is complete. The study nurse will record information in the patient-specific diary. If considered necessary, nurses can ask for an additional patient visit to the investigating centre. This is mandatory at suspected complete wound closure.

[figure not shown]

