### 3 STATISTICAL METHODOLOGY

#### 3.1 General Statistical Methodology

[figure not shown]
[figure not shown]
This study will use confirmative and explorative analyses. All analyses of primary and secondary variables will be performed on FAS. Subjects without any scheduled follow-up visit will not be included in any follow-up analyses. Complementary analysis of primary and secondary variables will also be performed based on PP population.

The primary analysis will be the comparison of Confirmed Complete wound Closure (CCC) between the two randomized groups using two-sided binary logistic regression analysis at significance level 0.05, on FAS with multiple imputation including the following covariates:

1. Country (as fixed effect)
2. Wound duration (<5 months;  $\geq$ 5 months)
3. Wound area after run-in period ( $<10 \text{ cm}^2$ ;  $\geq 10 \text{ cm}^2$ )

The essential analyses will be the comparison between the two randomised groups: the Granulox group and the Control group for primary and secondary variables. Analyses within each of the randomized groups will also be performed but without the same scientific value. For secondary efficacy variables the main analysis will be performed on change from baseline to final visit or at final visit, but analyses of change from baseline to the other visits will also be performed at week 1, 4, 8, 12 16 and 20. Final visit is defined as week 20 for subjects that have a 20 week visit, date of first CCC visit for subjects with CCC and for drop-outs with multiple imputation for week 20.

The study includes a fixed order of sequential testing of the following secondary variables.

The study utilized stratified randomization based on country, wound size, and wound duration. This is reflected by a stratified primary analysis adjusted for these variables. If baseline confounders are found, variables that differ between the two randomised groups and has a causal relation to the outcome variable, then complementary analyses will be performed adjusted for these variables.

For adjusted comparison between the two randomized groups, multivariable logistic regression will be used for dichotomous variables, analysis of covariance for continuous variables, Mantel-Haenszel pooling technique for ordered categorical variables and Cox proportional hazard model for time to event data.

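### Does it matter that the protocol names study site as a randomisation stratum in two places and country elsewhere?

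*Protocol*

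**What the plan says.** Five statements name the randomisation strata. All five include wound duration and wound area; they differ on the third factor.

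- Protocol 3.2: "Randomization will be stratified on study site, wound duration", followed by wound area. The reason given is residual variation in standard of care between sites.
- Protocol 5.2.2: "The study utilized stratified randomization based on site, wound size, and wound duration", followed by "This is reflected by a stratified primary analysis adjusted for these variables".
- Protocol 3.4.3, the section on assigning subjects: "Randomisation is centralized and stratified according to" a list of wound duration, wound area and country.
- SAP 1.2.1: "Randomization will be stratified on country, wound duration".
- SAP 3.1: "The study utilized stratified randomization based on country, wound size, and wound duration".

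The primary model is the same wherever it is specified. Protocol 5.2.2.1 lists "Country (as fixed effect") with the two wound factors, and SAP 3.1 and SAP 3.8.1 repeat the list. None has a site term. SAP 3.8.1 labels the three covariates as the stratified ones, and it also plans unadjusted closure results by country and by centre within country.

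**The concern.** Site and country are not two words for one thing. Protocol 3.1 plans several countries "with approximately 2-7 clinics per country", so the two descriptions are different randomisation schemes, and a central system can be programmed with only one of them. Protocol 3.2 also argues for its choice at site level, so the word does not look accidental when that section is read alone.

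If the stratum is site, Protocol 5.2.2 promises an adjustment that Protocol 5.2.2.1 does not deliver. Leaving a stratification factor out of the analysis usually makes the standard error of the treatment effect too large when that factor predicts the outcome. The test then becomes conservative and may lose power. With a binary closure endpoint, and with dressing sequences chosen clinic by clinic (Protocol 3.5.1.1), some between-site variation in closure is plausible. At stake would be the match between design and confirmatory model, and possibly some efficiency.

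**Working it through.** **1. Which factor do the documents support?**

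| Place | Third factor |
|---|---|
| Protocol 3.2, strata | site |
| Protocol 5.2.2, strata | site |
| Protocol 3.4.3, strata | country |
| SAP 1.2.1, strata | country |
| SAP 3.1, strata | country |
| Protocol 5.2.2.1, model | country |
| SAP 3.1, model | country |
| SAP 3.8.1, model | country |
| Protocol 5.2.2.3, sub-groups | country |

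On the strata alone the count is 2 for site and 3 for country; on the model it is 0 and 3. SAP 1.2.1 follows the paragraph in Protocol 3.2 closely, and SAP 3.1 follows the sentence in Protocol 5.2.2. In both, site has become country, while SAP 1.2.1 keeps the between-site reason. This fits an edit made in the SAP and in Protocol 3.4.3 but not carried through the rest of the protocol.

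**2. How different are the two schemes?**

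Strata = (countries or sites) × 2 duration levels × 2 area levels. N = 254 and 2 to 7 clinics per country come from Protocol 3.1. Seven countries is an assumption, because the protocol names seven only as examples.

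- Country: 7 × 2 × 2 = 28 strata; 254 / 28 = 9.1 patients per stratum.
- Site, lower end: 7 × 2 = 14 sites; 14 × 4 = 56 strata; 254 / 56 = 4.5.
- Site, upper end: 7 × 7 = 49 sites; 49 × 4 = 196 strata; 254 / 196 = 1.3.

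The ratio is 56 / 28 = 2 to 196 / 28 = 7, whatever the number of countries. These are averages at the extremes of the clinic range. They show that the schemes differ, but not that either harms the analysis.

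**3. Does the country-level model fail if site was the stratum?**

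The plan's sample-size inputs are redacted, so there is no stated power to reproduce. The question was put to a simulation instead, with these assumptions: 254 patients, 7 countries, 2 or 5 clinics in each, site effects with standard deviation 0.3 to 1.0 on the logit scale, and permuted blocks of 4 within strata. The analysis was the logistic model with country and the two wound factors.

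| Randomisation strata | Type I error, nominal 0.05 |
|---|---|
| Country | 0.047 to 0.061 |
| Site | 0.038 to 0.054 |

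Power under the two schemes differed by no more than about 2 percentage points. The site rows lean slightly to the conservative side, as theory predicts. The highest value, 0.061, occurs under country strata, where the model matches the design, so it is not a result of the mismatch.

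**The case for a change.** The strongest case for acting is that this is live text about the randomisation and the confirmatory model, and that it cannot all be true. A note in SAP section 5 on changes from the protocol, whose content is not visible, could not reconcile Protocol 3.2 and 5.2.2 with Protocol 3.4.3 and 5.2.2.1. The documents do not show what was programmed. If country was programmed, the correction is two wording changes, which is almost free.

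The contradiction stands, and so does the limit on what can be seen. What does not stand is the step from there to a needed change. On the probable reading the correction alters neither the randomisation nor the analysis, and analysts working from the SAP meet only country. On the other reading no remedy is clearly better than what is planned. Fixed site terms would put up to 49 sites into a logistic model with 254 patients, which invites sparse cells and unstable estimates; deleting the adjustment sentence only tidies the text. Sites are nested in countries, so the country term already adjusts for part of the between-site variation, and SAP 3.8.1 will show closure by centre.

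**Conclusion.** The inconsistency is real but clerical. Country is very probably the intended stratum, and the primary model then adjusts for every stratification factor, as Protocol 5.2.2 says it should. Had site been programmed, the country-level analysis would remain valid: simulated type I error was 0.038 to 0.054, and power was within about 2 points of that under country strata.

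The numerical part rests on seven countries, 2 or 5 clinics in each, between-site standard deviations of 0.3 to 1.0 on the logit scale, and blocks of 4. The visible text gives neither the allocation method nor the between-site variation. Much larger site differences would make the country-only test somewhat more conservative under site strata, which would cost power but would not inflate false positives. The two site phrases can be tidied whenever the protocol is next revised, but nothing in the design, the primary model or the interpretation of the result depends on it.
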